8.3 Secondary outcome statistics

To evaluate the effect of the StepIt exercises on VLU healing data from the control group will be compared with data from the StepIt group. The StepIt exercise data will be stratified into different groups according to coherence to treatment.

Healing is defined by the following parameters:

- Ulcer size
- PUSH score
- Mobility score
- Ankle range of motion
- Visual analogue pain score
- Charing Cross Venous Ulcer Questionnaire

To assess the Ulcer size, PUSH score and visual analogue pain scores which are measured every 6 weeks, the average difference between time points will be calculated per group. To compare the groups, Mann-Whitney U-test will be applied.

To assess mobility score and ankle range of motion, the average differences between first and last visit will be calculated. The control and intervention group will be compared by applying Mann-Whitney U-test or unpaired t-test depending on the distribution of the data.

To measure patient-reported outcome measures on quality of life at first visit and final visit, the Mann-Whitney U-test will be performed. Data of the control and intervention group will be compared by applying the Mann-Whitney U-test.

Subject to sufficient data being available, Cox proportional hazards regression analysis will be conducted to investigate the role of StepIt and other covariates in VLU healing rates. Other

covariates include: VLU size and age at baseline, ankle motion range, patient age, patient mobility, absence/presence of co-morbidities.

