PREVUE v4, dd 12Dec2018

PREVUE; PlantaR flexion Exercise for Venous Ulcer Evaluation, a multi-centre, controlled, prospective, randomized feasibility trial

Version 4, dd 12 December 2018

Chief Investigator's Statement of Ownership and Content.

I, [name], confirm that this protocol is my work and is owned by me. The protocol conforms with standards outlined in the Declaration of Helsinki 1964.

Name (PRINT):___[name]_____

Signature:

Date: ____12 Decl 2018_____

RESEARCH PROTOCOL SUMMARY

TITLE:	PREVUE; PlantaR flexion Exercise for Venous leg UlcEr, a multi- centre, controlled, prospective, randomized feasibility trial
Short title:	PREVUE
IRAS number	222694
Device description	StepIt plantar flexion rocker pedal device. CE-marked and licensed medical device. To be used in this study for indicated purpose, namely plantar flexion exercise.
Study design	Single centre, controlled, prospective randomized feasibility trial
Primary objective	To assess the feasibility of conducting a full RCT in the future - Participants' compliance to StepIt exercise regime
	 Recruitment and attrition rates, willingness of patients to be randomised, response rates to questionnaires, and degrees of missing data Testing of eligibility criteria and ability/willingness of clinical staff to partake in recruitment of participants Adequacy of duration of follow-up (e.g. in relation to VLU healing)
Secondary objectives	To determine the acceptability and efficacy of the step-it pedal as an adjuvant therapy for VLU at 6 and 12 weeks post-baseline - Healing rate (ulcer size, PUSH score) - Ankle motion range - Patient mobility score - VLU-related quality of life score - VLU-related pain - Patient feedback on use of the device
Patient population	A total of 28 participants, over the age of eighteen, with venous leg ulcers and treated either in hospital or at home by the community nursing team. Participants must have the capacity to provide informed written consent and complete patient reported outcome measures. Participants are recruited from the local community nursing caseload and identified in hospital clinics. - 12 Patient will receive treatment as usual (TaU) - 12 Patients will receive TaU plus StepIt exercise programme intervention

	Randomisation will be stratified for ulcer size, with cut-off PUSH
	score of up to 8, and 9 and above.
Sponsor	Cumbria Partnership NHS Foundation Trust
Manufactures O foundan	Charalle Coreboure A.D.
Manufacturer & funder	StepIt System AB,

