Participants will be randomised to either the control group (standard care) or the intervention group (standard care plus use of a StepIt pedal) for 12 weeks or until ulcer healing has taken place. Patients in both groups will be given the usual leg ulcer information leaflet, but those in the intervention group will be issued with a StepIt Pedal to use daily for foot and ankle exercises. These exercises consist of resisted plantar flexion while seated, performed 2 times daily in the pattern of: 1 minute exercise / 1 minute rest, 10 times (participants may alternate legs as an alternative to merely resting both legs for 1 minute). The participants will be asked to keep an exercise diary to record their activity. At their discharge visits participants are asked to provide their opinion on trial participation. All participants will have demographic data obtained and the following base line measures (table 2):

- VLU size measured with Convatec grid tool
- PUSH score (size and characteristics)
- Mobility score
- Ankle range of motion using a goniometer
- Visual analogue pain score
- Quality of life assessment using the Charing Cross Venous Ulcer Questionnaire

Table 3. Baseline measures

Weeks	0	2	4	6#	8	10	12#
Ulcer size and PUSH score	Х			Χ			Χ
Mobility score	Χ			Х			Χ
Ankle range of motion	Χ			Х			Χ
Visual analogue pain score	Χ			Χ			Χ
Charing Cross Venous Ulcer Questionnaire	Х			Х			Χ

Allowed to be up to 2 weeks early or late

The Pressure Ulcer Scale for Healing (PUSH) tool, see Appendix 1 is a standardised method of assessing and monitoring the severity and healing of both pressure ulcers and venous leg ulcers (Stotts et al, 2001; Ratliff & Rodeheaver 2005). Concerns have been raised regarding the criterion validity and intra-rater reliability of the tool (Pillen et al 2009) however in the absence of other valid tools it provides a comprehensive parallel assessment of the ulcer along with measuring size alone.

A mobility measure will be taken using a life space questionnaire, see Appendix 1 (Stalvey *et al* 1999). This is a tool that has demonstrated reliability and construct and criterion validity in establishing the spatial extent of an older person's mobility within their home setting. There are other versions (Peel *et al* 2005) that additionally measure the use of aids and equipment however this is not of particular interest within the study, hence the simpler version will be used.

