A recent review of specific health related quality of life instruments for venous leg ulcers favours the Charing Cross Venous Leg Ulcer Questionnaire (appendix 2) (Smith *et al* 2010) above others such as the Hyland for its disease specific psychometric characteristics (Gonzalez & Verdu 2011).

During the recruitment process the research team acts as a contact point and coordinator for patients requiring information and support. If concerns are raised on participants (mental) wellbeing based on the home visits or outcome of the assessments, referral of patients/families on to other professional agencies will be done as appropriate and according to the Trust guideline.

5.4 **Follow-up**

Patients are in the study until the VLU is healed or for the maximum period of 12 weeks. The patient will be followed up as they would in normal clinical practice. The community nurse will redress the VLU as per routine care, and will conduct the measurement of the VLU (grid measurement and PUSH score). The researcher will visit the patient at baseline, week 6 and week 12 of study participation to randomise the patient, hand out the StepIt pedal, measure ankle range of motion and conduct the questionnaires.

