6. SUBJECTS

6.1 Anticipated number of research subjects

Since there is no pilot data to base an *a priori* sample size calculation on, it is difficult to make a calculated prediction on the exact number of patients required for a sufficiently powered trial. The outcome of this present study will inform the power calculation for a larger definitive interventional trial. However, below a summary is given for the power potentially achievable for our suggested feasibility sample size. Since some patients may require surgical intervention or may withdraw, a hypothetical 30% dropout rate is calculated into the sample size (actual attrition rate is a study objective). A 1:1 allocation to the control and intervention group respectively will be applied.

The primary outcome, average percentage decrease in ulcer size is used for sample size calculation. Power calculations for sample size, 80% power and 5% significance, based on a Chi-squared test. A priori power calculations using GPower 3.1 software, result in the following sample size summarized in Table 4.

It must be stressed that this current PREVUE study will first and foremost establish if StepIt exercise is acceptable to staff and patients alike, and therefore it is not certain at this stage whether sufficient participants will be enrolled, if participants will be compliant and if they will be compliant for the 12 weeks treatment period.

Table 4, Sample size calculation

	Percentage patients achieving at least 50% reduction in ulcer size	Percentage patients not achieving 50% reduction in ulcer size		
Arm A (hypothetical)	60%	40%		
Arm B (hypothetical)	30%	70%		
	Power beta of 80%, Alpha p-value of 0.05, Effect size 0.6 Sample size required without any drop-out: 22 samples. Sample size with 30% attrition rate included: 28			
	Total of 28 patients: - 12 Patients to receive treatm - 12 Patient to receive treatment	nent as usual ent as usual plus Steplt exercise		

The CONSORT guidelines require a statement on the number of patients assessed for eligibility (Schulz, Altman & Moher 2010). The number of patients screened but who did not meet the inclusion criteria or who declined to participate will be recorded, as will any patients who are lot to follow-up (Appendix 3).

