APPENDIX 1. TOOLS AND ASSESSMENTS

This appendix contains:

- The PUSH tool that will be used to assess each leg ulcer at base line and 2 weekly thereafter. (from Stotts et al, 2001)
- The mobility life space questionnaire that will be completed for each participant to confirm limited mobility at base line and at 12 weeks (from Stalvey et al 1999)
- The Charing Cross Venous Ulcer Questionnaire used to score VLU-related quality of life for each participant at baseline and at 12 weeks (from Hareendran et al, 2005)
- Visual analogue pain scale

NATIONAL
PRESSURE
ULCER
ADVISORY
PANEL

Pressure Ulcer Scale for Healing (PUSH) PUSH Tool 3.0

Patient Name	Patient ID#	
Ulcer Location	Date	

Directions:

Observe and measure the pressure ulcer. Categorize the ulcer with respect to surface area, exudate, and type of wound tissue. Record a sub-score for each of these ulcer characteristics. Add the sub-scores to obtain the total score. A comparison of total scores measured over time provides an indication of the improvement or deterioration in pressure ulcer healing.

LENGTH	0	1	2	3	4	5	Sub-score
X	0	< 0.3	0.3 – 0.6	0.7 – 1.0	1.1 – 2.0	2.1 – 3.0	
WIDTH		6	7	8	9	10	
(in cm²)		3.1 – 4.0	4.1 – 8.0	8.1 – 12.0	12.1 - 24.0	> 24.0	
EXUDATE	0	1	2	3			Sub-score
AMOUNT	None	Light	Moderate	Heavy			
TISSUE	0	1	2	3	4		Sub-score
TYPE	Closed	Epithelial Tissue	Granulation Tissue	Slough	Necrotic Tissue		
							TOTAL SCORE

Life Space Questionnaire

Interviewer: "I am interested in all the places that you have been within the last 2 weeks" [It is acknowledged that original paper states 'within the last 3 days']

1.	During the past 2 week where you sleep?	s have you been to other rooms of your home besides the r	oom
	1 =Yes	2=No	
2.	During the past 2 week your porch, patio, garag	s have you been to an area immediately outside your home ge?	, such as
	1 =Yes	2=No	
3.	During the past 2 week courtyard, garden, driv	s have you been to an area outside your home such as a yar eway?	rd,
	1 =Yes	2=No	
4.	During the past 2 week beyond your own prop	s have you been to places in your immediate neighbourhoo erty?	d but
	1 =Yes	2=No	
5.	During the past 2 week but within your town o	s have you been to places outside your immediate neighbor community?	urhood
	1 =Yes	2=No	
6.	During the past 2 week community?	s have you been to places outside your immediate town or	
	1 =Yes	2=No	
7.	During the past 2 week	s have you been to places outside of Cumbria?	
	1 =Yes	2=No	

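### Healing is given a six-score definition that does not identify closure, on conflicting ulcer schedules, and there is no rule for how patients who leave on healing enter later comparisons

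*Protocol*

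**What the plan says.** **Definition.** Protocol section 8.3 states "Healing is defined by the following parameters" and lists ulcer size, PUSH score, mobility score, ankle range of motion, visual analogue pain score and the Charing Cross questionnaire. It gives no threshold, combination rule or closure criterion. The secondary objectives in the summary read "Healing rate (ulcer size, PUSH score" and list the other four measures separately. Section 6.1 brings in two more ulcer endpoints: "The primary outcome, average percentage decrease in ulcer size is used for sample size calculation" in the text, and "Percentage patients achieving at least 50% reduction in ulcer size" in Table 4.

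**Schedule.** Appendix 1 refers to "The PUSH tool that will be used to assess each leg ulcer at base line and 2 weekly thereafter". Table 3 (section 5.3) marks ulcer size and PUSH at weeks 0, 6 and 12 only, with a footnote on weeks 6 and 12: "Allowed to be up to 2 weeks early or late". Section 8.3 also describes these measurements as six-weekly.

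**Exit.** Section 5.4: "Patients are in the study until the VLU is healed or for the maximum period of 12 weeks".

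**Analysis.** Section 8.3 compares changes between time points for ulcer size, PUSH and pain. It uses the first and last visits for mobility and ankle range, and the first and final visits for quality of life. If the data suffice, a Cox model of healing follows. Its covariates include "VLU size and age at baseline, ankle motion range, patient age, patient mobility" and co-morbidity.

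**The concern.** A time-to-healing analysis needs a defined event and a date for it. The six-score definition supplies neither. A patient with a closed ulcer and an unchanged ankle range is not clearly healed under it, and a patient with less pain and an open ulcer is not clearly unhealed. How finely closure can be dated depends on which ulcer schedule is followed, and the protocol gives two.

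The exit rule adds a separate difficulty. Where a comparison uses the last visit, the length of follow-up depends on the outcome. Where it uses scheduled time points, patients who have healed may have no later value.

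These results carry weight. Section 8.2 uses the secondary outcome statistics to help decide whether a larger trial is indicated, and allows that the pilot might settle clinical effectiveness if the effect is large.

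**Working it through.** The protocol gives no expected number of healing events, so there is no figure of its own to reproduce here. The check sets the passages side by side and adds short arithmetic.

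**1. What counts as healed.**

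| Place | Healing or ulcer endpoint |
|---|---|
| Summary | ulcer size and PUSH |
| 6.1, text | mean percentage decrease in size |
| 6.1, Table 4 | at least 50% reduction, yes/no |
| 8.3, list | six scores, no rule |
| 8.3, Cox model | healing, no event given |

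None of these is closure. The PUSH form in Appendix 1 could express it: area 0, no exudate (0) and closed tissue (0) give a total of 0. No section says that this total is the event.

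**2. How often the ulcer is assessed.** Appendix 1: weeks 0, 2, 4, 6, 8, 10, 12 = 7 assessments. Table 3 and 8.3: weeks 0, 6, 12 = 3 assessments.

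**3. What the window does.** Week 6 may fall at weeks 4 to 8, and week 12 at weeks 10 to 14.
- Shortest gap between the two visits: 10 − 8 = 2 weeks.
- Longest gap: 14 − 4 = 10 weeks.

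These are the extremes, not typical values. A visit at week 14 also lies beyond the 12-week maximum in 5.4.

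**4. What exit at healing does.**
- *Mobility, ankle range, quality of life.* An unhealed patient's last visit falls at weeks 10 to 14. A patient who heals between the two follow-up visits may have a last measurement at weeks 4 to 8. Both enter the same comparison.
- *Healing before the week-6 visit.* Table 3 schedules no assessment at exit. Section 5.3 mentions a discharge visit, but only for the participant's opinion of the trial.
- *Ulcer size and PUSH.* A healed ulcer could be scored 0 at later time points, but the protocol does not say so.
- *Pain.* No value follows from closure, so it has to be measured.

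An illustration shows that the handling matters. It assumes exponential healing times, linear shrinkage to closure, 12 per arm, and 30% v 60% healed by week 12 (4,000 simulated trials). Scoring healed ulcers as 0 gives a difference in mean proportional reduction of 0.25 and Mann-Whitney power of about 46%. Giving healed leavers no week-12 value gives 0.18 and about 19%. With 40% v 70% healed, the figures are 0.21 and 39% against 0.17 and 12%. The healing curves are assumed and only ulcer size is covered.

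**5. The Cox model.** Terms: allocation, ulcer size, ulcer age, ankle range, patient age, mobility, co-morbidity (as one yes/no item) = 7. Patient age is listed separately, so the age paired with ulcer size is that of the ulcer. Neither the baseline list in 5.3 nor the characteristics in 8.1 includes it. The eligibility footnote requires only that the ulcer has been present for at least 2 weeks.

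Completers: 28 × (1 − 0.30) = 19.6. The protocol gives no healing proportion, so a range is assumed:

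| Assumed healed | Events | Events per term (7 terms) |
|---|---|---|
| 30% | 19.6 × 0.3 = 5.9 | 0.8 |
| 50% | 19.6 × 0.5 = 9.8 | 1.4 |
| 70% | 19.6 × 0.7 = 13.7 | 2.0 |

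If all 28 patients stayed and healed, the figure would be 28 / 7 = 4. The lay summary gives 48 patients instead: 48 × 0.70 = 33.6 completers, and 30% to 70% healed gives 10.1 to 23.5 events, or 1.4 to 3.4 per term.

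**The case against.** Much can be said for the plan, and it limits the point in six ways.

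- **The six scores are never combined.** Each has its own comparison, and each can be run. A reader might infer that healing cannot be analysed at all. That goes too far: the faults are the wording of the definition and the missing event.
- **Two coarse event times are not certain.** Under 5.4 the community nurse redresses and measures the ulcer as part of routine care, and patients stay until healed, so closure is presumably noticed when it happens. What stands is that no rule turns that record into a closure date.
- **Bias against StepIt is not shown.** A reader might infer that the later outcomes come mainly from StepIt's non-healers. The analyses of mobility, ankle range and quality of life use the last visit, which keeps healers in. The simulation shrinks the difference only for ulcer size, under assumed curves and with every healed patient dropped at week 12, which the protocol does not prescribe. Unequal follow-up and possible missing values stand; a direction does not.
- **Adequacy of 12 weeks can still be judged.** A reader might infer that this primary outcome is lost. Follow-up runs to healing or 12 weeks, so the proportion unhealed at the end is observable once healed is defined.
- **The Cox model is conditional, and covariate choice is often left to a SAP.** True, but 8.3 gives no criterion for sufficient data, and a SAP cannot supply an ulcer age that was never recorded. Baseline ankle range and mobility are legitimate covariates, even though both are also outcomes.
- **The visit window does not contradict Table 3.** Section 8.3 agrees with Table 3, so the schedule conflict lies with Appendix 1.

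**Conclusion.** The point holds as a fault in what the protocol states, not as a detail left to a SAP. Four of the six scores said to define healing do not measure closure, the summary contradicts that definition, and the Cox model has no event. Ulcer assessments number 7 or 3 depending on the section, with no rule for dating closure. Exit at healing makes some comparison periods depend on the outcome and may leave later values missing, with no stated handling and no established direction of bias. One Cox covariate is not listed as collected.

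The definition, schedule, exit and covariate findings rest on the text alone. The 0.8 to 2.0 events per term rests on N = 28, the protocol's hypothetical 30% attrition, an assumed 30% to 70% healed and co-morbidity counted as one term. Changes are warranted, but the separate group comparisons remain usable.

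**What to change.** 1. **Define healed once** as complete closure (area 0 and PUSH total 0), with a date taken from the community nurse's ulcer record. In 8.3, list mobility, ankle range, pain and quality of life as four separate outcomes.
2. **Reconcile Appendix 1 with Table 3 and 8.3** so that one ulcer and PUSH schedule stands.
3. **Amend the exit wording in 5.4** so that healed patients keep their planned week-6 and week-12 assessments. Score ulcer area and PUSH as 0 while the ulcer stays closed, and measure the other outcomes. This concerns data collection only, not treatment after healing.
4. **Compare the arms at fixed times**, not at the last visit, using actual assessment dates.
5. **Limit any Cox model** to allocation and baseline ulcer size. On the assumptions above that gives 5.9 / 2 = 2.9 to 13.7 / 2 = 6.9 events per term. This is still few, so the result should be read as descriptive.
6. **Collect ulcer duration at baseline**, or drop it from the covariates.

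The cost is a few extra visits to healed patients, one CRF item and minor protocol wording. The extra visits are not free, because 5.4 now ends participation at healing. Timing also matters: this version is dated 12 December 2018 and Table 2 ends recruitment in December 2018. For patients already finished, items 3 and 6 depend on what the clinical records hold, which the protocol does not say. The single definition, the reconciled schedule and the smaller model can still be adopted before analysis.

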8.2 Primary outcome statistics

The primary objective for this pilot study is the feasibility of conducting a larger scale randomised controlled trial. The secondary outcome statistics will inform the success of this pilot study and will therefore inform whether a larger scale trial is indicated. This will be based on signs of clinical effectiveness, positive patient feedback on the intervention, positive changes in VLU related quality of life, recruitment to time and target, low attrition rates, minimal data queries and lack of or low number of adverse events. If the effect size of the Steplt pedal is large enough, then this pilot trial may provide a definitive answer concerning its clinical effectiveness.

The following descriptive statistics will be reported on:

- Number of patients screened
- Number of patients eligible/ineligible, and percentage of patients consented into the trial
- Number of patients completed the trial/discontinued (plus reasons if discontinued)

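### Section 8.3 tests six unranked 'healing' outcomes with no deciding contrast, yet section 8.2 uses the results to judge effectiveness

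*Protocol*

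**What the plan says.** Section 8.3 lists six parameters under its definition of healing: ulcer size, PUSH score, mobility, ankle range of motion, visual analogue pain and the Charing Cross questionnaire. Each is compared between arms.

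- Ulcer size, PUSH and pain: "the average difference between time points will be calculated per group. To compare the groups, Mann-Whitney U-test will be applied". The section says they are measured every six weeks, and Table 3 puts the visits at weeks 0, 6 and 12. The interval to be compared is not named.
- Mobility and ankle range: change from first to last visit.
- Quality of life: first and final visit.

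A split by adherence and a possible Cox model come on top. The protocol summary sets the secondary objective as "To determine the acceptability and efficacy of the step-it pedal as an adjuvant therapy for VLU at 6 and 12 weeks post-baseline" and ranks neither week.

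Section 8.2 says how the results will be used: "The secondary outcome statistics will inform the success of this pilot study and will therefore inform whether a larger scale trial is indicated". It lists evidence of clinical effectiveness first among several considerations, and says a large enough effect could make the trial's answer on effectiveness definitive.

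Ulcer size has a special status in some places only. Section 6.1 calls average percentage decrease the primary outcome, while Table 4 uses the proportion with at least a 50% reduction. Section 6.1.1 calls size itself the primary outcome measure. Section 5.5.2 lists size as secondary, noting that it served the power calculation. None of these gives a time point.

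**The concern.** Unadjusted tests on secondary outcomes are normal in a feasibility trial and usually harmless, because nothing depends on them. Here something does. Section 8.2 makes these statistics part of the judgement on whether the pilot succeeded, and allows a definitive efficacy conclusion from them. With six outcomes of equal standing and, for three of them, an open choice of interval, an ineffective pedal has several chances to yield a favourable result. Ulcer size at week 6, PUSH at week 12 and pain over weeks 6 to 12 could each lead to a different conclusion. Nothing in the protocol fixes the choice before the data are seen, and section 6.1.1 says the researcher is not blinded.

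**Working it through.** **The plan's own figure.** Section 6.1 states: "Power calculations for sample size, 80% power and 5% significance, based on a Chi-squared test". Table 4 gives "Power beta of 80%, Alpha p-value of 0.05, Effect size 0.6" and "Sample size required without any drop-out: 22 samples. Sample size with 30% attrition rate included: 28". With one degree of freedom and N = 22, the noncentrality is 22 × 0.6² = 7.92 and the power at alpha 0.05 is 80.4%, so 22 is reproduced. Then 22 × 1.3 = 28.6, close to the stated 28. (Dividing by 0.7 would give 32.) This confirms 5% as the level for the sample size. It does not establish the level for section 8.3, which states none.

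**Counting the tests (section 8.3 with Table 3).**
- One change per outcome: 6.
- Adding a second interval for ulcer size, PUSH and pain: 6 + 3 = 9.
- All three pairwise intervals for those outcomes: 3 × 3 + 3 = 12.

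The adherence strata and the Cox model are not counted. Appendix 1 speaks of PUSH every two weeks, which would add intervals; I used the six-weekly schedule of 8.3 and Table 3.

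**Upper reference, independent tests.** The chance of at least one significant result is 1 − 0.95^k in either direction, and 1 − 0.975^k favouring the pedal.
- k = 6: 26.5% and 14.1%
- k = 9: 37.0% and 20.4%
- k = 12: 46.0% and 26.2%

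**Allowing for correlation.** The protocol gives no correlations, so they are assumed. The set-up is: no device effect; 12 per arm (the arm size in Table 4); six outcomes with a common correlation of 0.3 to 0.8, each scored so that higher is better; independent changes over weeks 0–6 and 6–12; Mann-Whitney tests at two-sided 5%. All six outcomes are tested over weeks 0–12. Nine tests add weeks 0–6 for the three repeated outcomes, and twelve also add weeks 6–12. The first figure in each cell is for correlation 0.3 and the second for 0.8.

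| Tests | At least one favouring the pedal | At least one in either direction |
|---|---|---|
| 1 (nominal) | 2.5% | 5% |
| 6 | about 11% to 6% | about 22% to 13% |
| 9 | about 15% to 10% | about 30% to 20% |
| 12 | about 18% to 12% | about 36% to 25% |

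A repeat of the simulation agreed to within about one percentage point.

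**Sensitivity.** A different structure (between-visit correlation 0.5, between-outcome correlation 0 to 0.7, 12 per arm) gives 13% to 8%, 19% to 14% and 22% to 16% favouring the pedal for 6, 9 and 12 tests. With 14 per arm these rise by at most about two points.

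**After the fix.** One named contrast has a simulated either-direction error rate of 4.1% to 5.2%. The exact Mann-Whitney size at 12 per arm is 4.5%.

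**The case against.** The strongest objection is that multiplicity handling and exact secondary contrasts commonly belong in a statistical analysis plan, which is not at hand, and that 5.5.2 calls the efficacy results preliminary. This stands to the extent that the lack of an alpha split is not in itself a fault of the protocol. It does not dispose of the point. The decision role in 8.2, the equal weight in 8.3 and the conflicting status of ulcer size are all in the protocol text, and an adjustment made elsewhere would leave that text unchanged.

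Four stronger readings are tempting, and the document does not support them.

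- *Every test is made at 5%.* Only the sample-size section states 5%. For 8.3 it is an assumption.
- *Nine to twelve tests are prescribed.* The wording in 8.3 can mean one average change per outcome, which gives six. Section 8.2 also lists quality of life apart from clinical effectiveness. Leaving it out gives five tests, or 1 − 0.975^5 = 11.9% favouring the pedal if they were independent.
- *The either-direction rates measure the risk.* A result against the pedal is not evidence that it works, so the favourable-direction figures are the relevant ones.
- *The trial would wrongly progress this often.* Section 8.2 weighs feedback, quality of life, recruitment, attrition, data queries and adverse events as well. It nowhere says that one small p-value triggers a larger trial, so no false-progression rate can be derived.

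Nor is it right that no lead outcome exists. Ulcer size is called primary in 6.1 and 6.1.1. What is missing is one form, one time point and any precedence in 8.2 and 8.3.

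**Conclusion.** The point holds in this limited form. Section 8.2 draws on the section 8.3 comparisons to judge effectiveness, and those comparisons have no deciding outcome-by-time contrast. Under the stated assumptions, the chance of at least one nominally significant result favouring an ineffective pedal is about 6% to 11% on the plainest reading (six tests), rising to 12% to 18% with twelve. That is roughly two to seven times the 2.5% for a single test (6/2.5 = 2.4; 18/2.5 = 7.2). The exact values depend on correlations the protocol does not give and on a 5% level it states only for the sample size. The direction of the problem is the same on every reading tried. It bears on how efficacy results may be cited. It does not show how often the programme would wrongly go ahead.

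**What to change.** 1. In 8.3, name one efficacy contrast: percentage change in ulcer area (Convatec grid) from baseline to week 12, compared between arms. This is the form named in the text of 6.1. Count ulcers healed before week 12 as a 100% reduction, since section 5.4 ends participation at healing.
2. Reconcile 6.1 (including the 50% reduction in Table 4), 5.5.2 and 8.3 to that one form, and bring the description of ulcer size in 6.1.1 into line.
3. Label the other five outcomes and the other ulcer-size intervals exploratory. Report them as estimates with 95% confidence intervals and make no significance claim.
4. In 8.2, tie the clinical-effectiveness criterion, and any claim of a definitive answer, to the named contrast only.

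The cost is a few sentences of protocol wording, with no extra patients or data. The downside is that a chance-significant result on another outcome can no longer be cited as evidence of effectiveness. Naming the contrast limits chance findings; it does not show that the trial has adequate power for it, which is a separate question.
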